* Axial T1-weighted LAVA-FLEX acquired in Part1. may be used for pre-contrast T1-weighted images.

Image review:

- PET/MR fusion study, including PET emission data, MRAC image and focused pelvis PET/MR fusion images will be sent to MIM Vista workstation for review by an independent, experienced board certified nuclear medicine radiologist without knowing clinical findings except for high risk prostate cancer.
- Focused mpMRI of pelvis images will be sent to PACS for review by an independent, experienced board certified body MR radiologist without knowing clinical findings except for high risk prostate cancer.

Evaluation of imaging findings:

Reviewers review images to evaluation imaging findings without knowing clinical findings except all subjects are recently diagnosed with very high-risk or high-risk prostate cancer. Readout workflow is illustrated in Figure 2. The scores will be recorded and stored in a secured REDCap file.

Pelvic mpMRI:

1. Lesion detection and characterization utilizing PI-RADS version 2 (15).
2. Tumor staging utilizing AJCC TNM staging system (3)
3. Detection of suspicious pelvic lymph nodes.
4. Detection of suspicious osseous lesion in the pelvis.

Torso and focused C-11 choline PET/MR:

1. Lesion detection and characterization.
2. Tumor staging
3. Detection of suspicious pelvic and extrapelvic lymph nodes.
4. Detection of suspicious osseous lesion in the pelvis and extrapelvic regions.
5. Document SUV in the region of interest (ROI) if possible.

Reference standards

[figure not shown]
[figure not shown]

1. Histopathology results when available
2. Clinical imaging study (CT, bone scan, etc).
3. Clinical follow-up (progression or regression at follow-up routine clinical imaging after treatment).

Prostate tumor localization and characterization: Focused C-11 choline PET/MR and pelvic mpMRI findings to be correlated with clinical prostate biopsy and surgery results.

Lymph node metastases: Torso and focused C-11 choline PET/MR and pelvic mpMRI findings to be correlated with clinical CT, lymph node biopsy, and surgery results

Bone metastases: Torso and focused C-11 choline PET/MR and pelvic mpMRI findings to be correlated with whole body bone scan, F-18 NaF PET/CT (if available), CT, dedicated MRI, and biopsy results.

Figure 1. Illustration of Part 1 “Torso C-11 Choline PET/MR” and Part 2 “Hybrid Focused C-11 Choline PET/MR and Pelvic mpMRI.”

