Acquisition time per table bed	Part 1: Torso C-11 choline PET/MR				Part 2: Hybrid dedicated focused C-11 choline PET/MR and pelvic mpMRI			
2-5 min/bed	PET		AC	Diagnostic MR pulse sequences				
2-5 min/bed	PET		AC	Diagnostic MR pulse sequences				
2-5 min/bed	PET		AC	Diagnostic MR pulse sequences				
2-5 min/bed	PET		AC	Diagnostic MR pulse sequences				
2-5 min/bed	PET		AC	Diagnostic MR pulse sequences				
2-5 min/bed	PET				Focused C-11 choline PET/MR 		Pelvic mpMRI (anatomic and functional sequences) without e-coil	
Time	25-30 min				45-50 min			

AC=attenuation correction

mpMRI = multiparametric MRI

e-coil = endorectal coil (for illustration purpose only, will not be used in current study)

* = F-18 FDG PET/MR shown for illustration purpose

** = C-11 choline PET/CT shown for illustration purpose

*** = T2W shown for illustration purpose

Figure 2. Workflow of Readout Sessions (parts 1-3)

[figure not shown]

Table 1. Summary of imaging finding evaluation

	C-11 choline PET/MR (research)	Clinical imaging exams	Reference standard	Findings
Local T staging: Prostate	Focused pelvic C-11 choline PET/MR	Pelvic mpMRI	Pathology results (biopsy, surgery if available)	Localization Characterization Local tumor (T) staging
Metastasis to pelvic lymph nodes(N)				
Pelvis	Focused C-11 choline PET/MR	Pelvic mpMRI CT	Pathology results (biopsy, surgery if available)	Localization SUV values
Torso	Torso C-11 choline PET/MR	CT	Pathology results (biopsy, surgery if available)	Localization SUV values
Metastasis to pelvic bone (M)				
Pelvis	Torso and focused C-11 choline PET/MR	Pelvic mpMRI CT Bone scan	Pathology results (biopsy, surgery if available)	Localization SUV values
Extra-pelvis	Torso C-11 choline PET/MR	CT Bone scan	Pathology results (biopsy, surgery if available)	Localization SUV values
Visceral metastasis (M)				
Visceral metastasis (M)	Torso C-11 choline PET/MR	CT	Pathology results (biopsy, surgery if available)	Localization SUV values

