3.4 Primary Study Endpoints

Patient: Completion of all imaging examinations with laboratory results.

Data analysis:

Objective 1: Descriptive study. With biopsy and/or surgical histopathology as gold standard, the sensitivity, specificity and accuracy of PET/MR will be calculated.

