7.2 Statistical Methods

Descriptive Statistics

Descriptive statistics will be used to describe the average time of the total procedure, patients' tolerance and satisfaction level about the procedure. Paired t-test will be used to compare the suspicious lymph nodes and suspicious osseous lesions in the pelvis and extrapelvic regions detected by hybrid C11-choline PET/MR and pelvic multiparametric MRI method and by conventional CT and bone scan to investigate if the new method is able to detect more lymph nodes and osseous lesions compared to the conventional method. Paired t-test will also be used to compare the average SUV of lymph nodes and osseous lesions in the pelvis and extrapelvic regions by new method with that by conventional method to investigate if the new method provided more clarity in terms detecting the lymph nodes and lesions compared to the old method. If the patients' biopsy and surgery results available, sensitivity, specificity, positive predictive value and negative predictive value of detecting malignant lymph nodes and osseous lesions by the new method and by conventional method will be estimated and compared using McNemar's test.

Handling of Missing Data

As the sample size is 20 and imaging is completed over one day, no missing imaging data is anticipated.

Multiplicity

In current project, there is one primary objective and we don't have to adjust for multiple comparison.

Interim Analysis

There will not be interim analysis for the study.

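### Nodal and bone accuracy is estimated only in subjects whose routine care yields pathology, with no rule for the rest, so sensitivity and specificity are at risk of partial-verification bias and the power statement assumes that all 20 are verified

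*Combined protocol and SAP*

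**What the plan says.** - **Accuracy analysis (Section 7.2).** It is conditional: if "biopsy and surgery results available, sensitivity, specificity, positive predictive value and negative predictive value of detecting malignant lymph nodes" and osseous lesions "will be estimated and compared using McNemar's test". The comparison is between the hybrid method and conventional CT with bone scan.
- **Source of pathology.** Section 3 takes histopathology from standard care. The Section 6.4 schedule contains no nodal or bone sampling.
- **Reference standard.** Section 3.4 reads "With biopsy and/or surgical histopathology as gold standard, the sensitivity, specificity and accuracy of PET/MR will be calculated". Table 1 in Section 3.3 gives "Pathology results (biopsy, surgery if available" for every region. The reference-standard list in Section 3.3 starts with "Histopathology results when available" and then adds clinical imaging (CT and bone scan among others) and clinical follow-up. Section 7.2 does not use the last two.
- **Missing data (Section 7.2).** The only statement is "As the sample size is 20 and imaging is completed over one day, no missing imaging data is anticipated".
- **Analysis population (Section 7.3).** Completers of the study procedures and follow-up. A reference result is not named as a condition.
- **Power (Section 7.1).** 82% for a two-sided 0.05 McNemar's test with 20 patients, an accuracy difference of 0.3 and a discordant proportion of 0.31, for detecting patients with malignant nodes.

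**The concern.** The reference result is the item most likely to be absent. Every subject gets the scans, but only some will have nodes or bone sampled, and the plan does not say what happens to the others. As written, they drop out of the accuracy analysis.

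If the verified subjects were a random part of the 20, the only cost would be precision. But staging images are obtained to guide management (Sections 1.1 and 4.1), so they may well influence who is biopsied or operated on. Sensitivity and specificity in the verified subset then mix test performance with patient selection. If selection follows one method more than the other, the between-method contrast is affected too, and that contrast is the added value the secondary objectives ask about. The plan requires no report of who went unverified, so a reader could not judge this.

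**Working it through.** **1. The plan's own figure.** Miettinen's formula for McNemar's test, with d = 0.30, ψ = 0.31 and n = 20 (Section 7.1):

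power = Φ[(d√(nψ) − 1.96ψ) / √(ψ² − d²(3+ψ)/4)]
= Φ[(0.7470 − 0.6076) / 0.1471] = Φ(0.948) = 82.8%.

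The stated 82% is reproduced, with all 20 subjects contributing a reference result.

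**2. The same calculation with fewer verified subjects.** The documents give no verification rate, so m is an assumption.

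| Verified m | Formula above | Exact McNemar |
|---|---|---|
| 20 | 82.8% | 56.9% |
| 16 | 66.0% | 33.8% |
| 12 | 42.2% | 12.1% |
| 10 | 29.5% | 5.0% |
| 8 | 17.9% | 1.2% |

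**3. One test.** Let v1 and v0 be the verification rates in test-positive and test-negative subjects.

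apparent Se = Se·v1 / [Se·v1 + (1−Se)·v0]; apparent Sp = Sp·v0 / [Sp·v0 + (1−Sp)·v1].

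Assumed true Se 0.60, Sp 0.90:
- v1 = 0.8, v0 = 0.3: Se = 0.48/0.60 = 0.80; Sp = 0.27/0.35 = 0.77.
- v1 = 0.3, v0 = 0.8: Se = 0.18/0.50 = 0.36; Sp = 0.72/0.75 = 0.96.
- v1 = v0: both unchanged.

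Here verification depends only on this test's result. PPV and NPV condition on that result, so they are unbiased.

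**4. Two methods.** Assumed: hybrid Se 0.70, conventional Se 0.40, both Sp 0.90, conditional independence, nodal prevalence 0.3. True sensitivity gap 0.30; true accuracy difference 0.84 − 0.75 = 0.09.

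| Verification rule | Expected verified | Hybrid Se | Conventional Se | Gap | Accuracy difference |
|---|---|---|---|---|---|
| 60%, unrelated to imaging | 12.0 | 0.70 | 0.40 | 0.30 | 0.09 |
| 80% if conventional positive, 30% if negative | 7.9 | 0.70 | 0.32/0.50 = 0.64 | 0.06 | 0.824 − 0.722 = 0.10 |
| 30% if conventional positive, 80% if negative | 14.1 | 0.70 | 0.12/0.60 = 0.20 | 0.50 | 0.849 − 0.766 = 0.08 |
| 80% if either positive, 30% if neither | 9.8 | 0.56/0.71 = 0.79 | 0.32/0.71 = 0.45 | 0.34 | 0.794 − 0.647 = 0.15 |

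The sensitivities do not depend on prevalence; the number verified does.

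**5. Discordant pairs among subjects with disease.** True split, hybrid-only to conventional-only: 0.70×0.60 to 0.30×0.40 = 0.42 to 0.12, or 3.5 to 1.
- Row 2: 0.42×0.3 to 0.12×0.8 = 0.126 to 0.096, or 1.3 to 1.
- Row 3: 0.42×0.8 to 0.12×0.3 = 0.336 to 0.036, or 9.3 to 1.
- Row 4: every discordant pair has one positive test, so all are verified at 80% and the split stays 3.5 to 1.

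**6. How far simple bounds reach.** In row 2 the expected counts are 3.0 verified with disease, 4.9 verified without and 12.1 unverified, of whom 3.01 are hybrid-positive and 0.76 conventional-positive.
- Unverified all negative: sensitivities unchanged, gap 0.06.
- Unverified all positive: hybrid (2.10 + 3.01)/15.1 = 0.34; conventional (1.92 + 0.76)/15.1 = 0.18; gap 0.16.

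Neither setting reaches the true 0.30. The limits come from treating the four result combinations separately. With only the 2.646 unverified hybrid-only subjects set positive, the gap is (3.402 − 0.576)/5.646 = 0.50. With only the 0.396 unverified conventional-only subjects set positive, it is (0.756 − 0.972)/3.396 = −0.06.

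**The case against.** The strongest reply is that no bias has been shown. No section says how subjects are chosen for nodal or bone sampling, or whether PET/MR readings reach the treating clinicians, and Section 4.3 allows PET/MR before or after routine imaging. If verification is unrelated to imaging, the bias is zero. This stands: the point is a risk and an absent rule, not a demonstrated bias.

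A reader might also infer four stronger things that the documents do not support.
- **All four accuracy measures are biased.** Not so where verification depends on one test alone: that test's PPV and NPV are then unbiased.
- **The Section 7.1 comparison is necessarily distorted.** Not so. If verification follows either test being positive, the split of discordant pairs is preserved. With verification by the conventional result, the overall accuracy difference moved only from 0.09 to 0.10 or 0.08. The certain effect on 7.1 is fewer evaluable subjects whenever any lack a reference result.
- **The plan asserts that nothing will be missing.** It says "no missing imaging data is anticipated", which is limited to imaging and silent on pathology.
- **Follow-up should replace pathology as the main reference, since Section 3.3 lists it.** That standard is change on routine imaging after treatment. It may reuse CT or bone scan, which are the comparator, and treatment can change a node's appearance. No window is given: scheduled contact ends with the Day 2 call, and the stated study duration is 16 weeks. It would also displace the gold standard of Section 3.4.

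Finally, the lesion-count comparison in Section 7.2 does not need pathology, so it is outside this point.

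**Conclusion.** The point holds as a risk that the plan leaves unmanaged. Three facts come from the text: accuracy is conditional on routine-care pathology, no rule covers unverified subjects, and the sample-size statement counts all 20. That verification follows imaging is an inference.

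Under the assumed rates, a true sensitivity gap of 0.30 can appear as anything from 0.06 to 0.50 across the patterns tried, and one test's Se and Sp of 0.60 and 0.90 as 0.80 and 0.77 or 0.36 and 0.96. These figures rest on assumed accuracy, verification rates and, for two methods, conditional independence. They show direction and scale and do not predict this trial's result. The loss of power to 42.2% at 12 verified subjects uses the plan's own inputs, with only the 12 assumed.

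The change should be made, because without it a reader cannot separate imaging performance from patient selection.

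**What to change.** In Section 7.2:
1. Keep pathology as the primary reference, as in Section 3.4.
2. Tabulate verified and unverified subjects by the four hybrid × conventional result combinations, separately for nodes and bone.
3. Report sensitivity, specificity and the paired comparison in verified subjects, then over all imaged subjects with the unverified set all negative and all positive. Label these as two settings rather than limits, and take the smallest and largest values over allocations within the four combinations from the same table (see step 6 of the working). Reconcile the all-imaged set with the completers-only population in Section 7.3.
4. Extend the missing-data paragraph to the reference result.
5. Use the Section 3.3 follow-up standard, if at all, as a supportive analysis only, with a stated window and a reading that does not use the CT, bone scan or PET/MR under comparison.

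In Section 7.1, state that the 82% holds only if all 20 subjects have a reference result.

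The cost is wording, a little more analysis and some chart review, with no added procedures for subjects. The downside is wider and less favourable ranges, which is what partly verified data on 20 subjects can support.

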1.5 Risks and Benefits

C-11 choline is involved in phosphorylation process integrated into phospholipids in the cell membrane as part of phosphatidylcholine, which is vital in prostate cancer cell. The main risk involves the exposure to the radioactivity associated with the C-11 isotope incorporation. This exposure has been calculated to be much lower than the F-18 FDG. In addition, there is no radiation risk related to MR scan. For MR safety concern, each subject will undergo MR safety screening performed by PET/MR technologist prior to imaging.

2 Study Objectives

Primary Objective:

- 1) Test whether a hybrid combination of focused C-11 choline PET/MR and pelvic mpMRI on a PET/MR system is feasible

Secondary Objective(s):

- 1) Determine the efficacy (added values) of a hybrid combination of molecular focused C-11 choline PET/MR and functional and anatomic pelvic mpMRI in comparison with clinical findings.
- 2) Determine the efficacy (added values) of a torso C-11 choline PET/MR in comparison with conventional CT and bone scan in depicting metastasis to lymph node and bone.

3 Study Design

This study will be a prospective study to test and optimize the feasibility of hybrid 3T PET/MR scan in diagnosing and staging high and very high risk prostate cancer patients.

The FDA approved C-11 choline PET tracer at a dose of 12-14 mCi will be administered intravenously prior to fused PET/MR scan, and prior to diagnostic pelvic mpMRI scan while patient lying in the scanner.

In addition, single dose of Gadavist® (Gadobutrol, Bayer) is at no more than 0.1 mmol/kg will be administered intravenously for pelvic mpMRI.

The whole imaging procedure will be conducted on an FDA approved GE SIGNA 3T PET/MR scanner.

The C11-choline PET/MR and pelvic mpMRI findings and results will be compared with serum PSA level, Gleason score, clinical CT and nuclear medicine whole body bone scintigraphy findings, and histopathological results obtained through standard of care management.

Our primary interest is to investigate the feasibility of hybrid C11-Choline PET/MR fusion and pelvic mpMRI in imaging primary prostate cancer.

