7.1 Sample Size Determination

Our null hypothesis is the hybrid C11-choline PET/MR and pelvic multiparametric MRI will have an equal accuracy of detecting patients with malignant lymph nodes in the very high risk/high risk prostate cancer patients compared to that in the conventional CT and bone scan method. With 20 patients, a McNemar's test with a 0.05 two-sided significance level will have 82% power to reject the null hypothesis if the difference in accuracy of the two methods is 0.3 or greater and assume discordant pairs is expected to be 0.31.

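### The reason for waiving multiplicity control (a single primary objective) does not cover the planned tests, and the one powered test is missing from section 7.2

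*Combined protocol and SAP*

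**What the plan says.** The multiplicity paragraph in section 7.2 gives as its reason "In current project, there is one primary objective", and concludes from this that no adjustment is needed.

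The primary objective in section 2 is: "Test whether a hybrid combination of focused C-11 choline PET/MR and pelvic mpMRI on a PET/MR system is feasible". Its endpoint in section 3.4 is "Patient: Completion of all imaging examinations with laboratory results". The data analysis given there for objective 1 is labelled descriptive, and "the sensitivity, specificity and accuracy of PET/MR will be calculated". Section 7.2 describes procedure time, tolerance and satisfaction without any test. No success threshold is attached to feasibility.

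The tests lie elsewhere:

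- Section 7.1 sets the sample size on a comparison with CT and bone scan: "Our null hypothesis is the hybrid C11-choline PET/MR and pelvic multiparametric MRI will have an equal accuracy" for finding patients with malignant nodes. It specifies McNemar's test, N = 20, two-sided 0.05 and 82% power.
- Section 7.2 plans paired t-tests on suspicious node and bone-lesion counts, in the pelvis and outside it.
- It continues: "Paired t-test will also be used to compare the average SUV of lymph nodes and osseous lesions", for the new method against the conventional one.
- If pathology is available, it plans McNemar comparisons of sensitivity, specificity, PPV and NPV for nodes and bone. Accuracy is not in that list.

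The matching aim in section 2 is secondary objective 2: "Determine the efficacy (added values) of a torso C-11 choline PET/MR in comparison with conventional CT and bone scan". Section 3.5 declares no secondary endpoints.

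**The concern.** Having one primary objective is a sound reason not to adjust when that objective carries the one test on which a conclusion rests. Here the objective carries no test, so the argument gives no protection to the comparisons that will produce p-values.

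Section 7.2 attaches conclusions to several of these comparisons: whether the new method finds more nodes and bone lesions, and whether it shows them more clearly. Section 13 makes publication depend on what the data analysis justifies. With no test marked as the one that supports a claim, any nominally significant result could be reported as evidence that PET/MR detects more disease. The powered comparison would then have no more standing than the rest, and it currently has no entry in the methods section.

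**Working it through.** **1. The plan's own figure.** Inputs from section 7.1: n = 20, difference d = 0.30, discordant proportion ψ = 0.31, two-sided alpha 0.05 (z = 1.96).

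- Miettinen approximation: Φ[(d√(nψ) − zψ) / √(ψ² − d²(3+ψ)/4)] = 82.8%.
- Wald form: Φ[d√n / √(ψ − d²) − z] = 81.6%.

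The stated 82% is reproduced. So section 7.1 does contain a real inferential test, and it belongs to the comparison with CT and bone scan.

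**2. Counting the tests in 7.1 and 7.2.**

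| Family | Tests |
|---|---|
| Nodal accuracy, McNemar (7.1) | 1 |
| Count t-tests, node and bone | 2 pooled, 4 split by region |
| SUV t-tests, node and bone | 2 pooled, 4 split by region |
| McNemar: 4 measures × node and bone | 8 |

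The total is 1 + 2 + 2 + 8 = 13, or 1 + 4 + 4 + 8 = 17.

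Not all of these can be run as written. No SUV is defined for CT or bone scan, so the SUV tests have no paired comparator. PPV and NPV have denominators that differ between methods, so McNemar's test does not apply to them. That leaves 1 accuracy test, 2 to 4 count t-tests and 4 sensitivity/specificity tests, which is 7 to 9. If pathology is not available, only the 2 to 4 count t-tests remain.

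**3. Chance of at least one false positive.** Assume all nulls true, independence and size 0.05 for each test. The formula is 1 − 0.95^k.

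| k | Result |
|---|---|
| 2 | 9.8% |
| 4 | 18.5% |
| 7 | 30.2% |
| 9 | 37.0% |
| 13 | 48.7% |
| 17 | 58.2% |

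**4. Allowing for the true size of McNemar's test.** At n = 20 and ψ = 0.31, the size is 0.0138 (exact) or 0.0478 (uncorrected). Sensitivity and specificity split the patients by disease status. Assuming 10 with and 10 without disease at the same ψ, the size is 0.0015 (exact) or 0.035 (uncorrected).

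- Exact, 7 tests: 1 − 0.95² × (1 − 0.0138) × (1 − 0.0015)⁴ = 11.5%.
- Exact, 9 tests: 1 − 0.95⁴ × (1 − 0.0138) × (1 − 0.0015)⁴ = 20.2%.
- Uncorrected, 7 tests: 1 − 0.95² × (1 − 0.0478) × (1 − 0.035)⁴ = 25%.
- Uncorrected, 9 tests: 1 − 0.95⁴ × (1 − 0.0478) × (1 − 0.035)⁴ = 33%.

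Together with step 3, the 7 to 9 computable tests give about 12 to 37%.

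**5. Allowing for correlation.** Simulated two-sided z-tests of size 0.05 with a common correlation of 0.3 to 0.7 give 20 to 33% for 9 tests, 24 to 42% for 13 and 27 to 49% for 17.

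**The case against.** The strongest case on the other side has four parts.

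**This is a 20-patient pilot, and unadjusted secondary comparisons are common in pilots.** That stands as a reason not to demand alpha adjustment, and none is asked for here. It does not rescue the stated reason, because section 7.1 sets a null hypothesis, an alpha and a power, and so intends inference.

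**The plan already hints at an exploratory reading.** The synopsis promises descriptive statistics, and the tests in 7.2 appear under a descriptive heading. This is a hint only. Nothing labels the tests exploratory, and 7.2 says what several of them are meant to show.

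**The split between primary and secondary is not clean.** This stands in part. Section 3.4 places sensitivity, specificity and accuracy under the primary endpoint, so it would be wrong to say that everything compared is purely secondary. But they are only calculated there. If they were primary, there would be several primary measures, and the waiver would still fail. It would also be wrong to say that no hypothesis is identified: 7.1 states one. It is not designated as the sole basis for a claim, and 7.2 does not carry it.

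**The error rate is easily exaggerated.** This stands. A reader might infer roughly even odds of a false positive. That needs 13 to 17 independent tests, each with true size 0.05. The documents state 0.05 only for the 7.1 test. Some of the counted tests cannot be run, the McNemar set depends on pathology, and the exact version is conservative at this sample size. All tests draw on the same 20 patients, so correlation is expected.

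**Conclusion.** The point holds. The waiver rests on an objective that is not tested, while all planned tests concern the comparison with CT and bone scan. The one powered hypothesis is absent from the methods section. This follows from the text alone and does not depend on any error-rate figure.

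The size is moderate and uncertain. Assuming 0.05 for every test and all nulls true, the chance of at least one false positive is about 10 to 19% with only the count t-tests and about 12 to 37% with the 7 to 9 computable tests. The second range depends on the McNemar version and, at its lower values, on an assumed 10/10 disease split. Both ranges assume independence and would fall with positive correlation. The 49 to 58% range is an upper bound. The documents do not support even odds as the expected figure, but the independence-based figures are all well above 5%. The pilot setting limits the consequence to what may be claimed from the results.

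**What to change.** Replace the multiplicity paragraph in section 7.2 with text that says three things:

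1. The primary feasibility objective is analysed descriptively and carries no hypothesis test.
2. The per-patient nodal accuracy comparison of section 7.1, by McNemar's test at two-sided 0.05, addresses secondary objective 2 and is the only hypothesis test that supports a comparative claim. Add this test to the methods in 7.2 and say which version of McNemar's test will be used, because the version changes its size.
3. All other comparisons are exploratory and are reported as estimates with 95% confidence intervals, without significance statements.

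Section 3.5 should be brought into line, since it now lists no secondary endpoint for this test to belong to.

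The cost is about a paragraph of text, with no extra patients and no alpha penalty. The price is that the remaining p-values cannot be presented as findings. The change does not settle two neighbouring matters: the named test needs a reference result for each patient, while section 3.3 offers histopathology only when available; and the SUV, PPV and NPV comparisons still need a workable definition.
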